Other groups have begun to look at DTI as a methodology to examine the changes in the brain in children with craniosynostosis, but in older children^{9 11}, this group found that, "Although these patients have a normal fiber organization, increased diffusivity parameters suggest abnormal microstructural tissue properties of the investigated white matter tracts." Thus far, only animal studies demonstrate the effect of the CVR in a rabbit model of craniosynostosis, which suggests enhanced white matter tracts following intra-cranial expansion^{12, (12)} As this is a pilot study, we will plan to recruit our own control subjects, age matched to our test subjects, but also plan to compare them with de-identified publicly, available datasets, i.e., the Baby Connectome project once they are made available.¹³ Our hypothesis is that CVR has a positive effect on white matter tract development and our proposed study seeks to perform the first human study of the relevant patient population.

Study Aims

Aim 1: We will *establish* pilot data to establish a normative curve of white-matter tract development in normal children under 4 years of age using (DTI). Fractional anisotropy (FA) (a main DTI parameter sensitive to white matter integrity) maps will be created to achieve a normative "white matter change curve" with from infancy to pre-school age.

Aim 2: Will *quantify* the change in white matter tract organization after cranial vault remodeling (CVR) surgery in patients with craniosynostosis by analyzing pre- and post-operative DTI data. This experimental cohort will also be examined in comparison to age-matched controls as compiled in Specific Aim #1, pooled with other centers and compared with published data sets of normal babies from the Baby Connectome Project. . The imaging will be repeated at three intervals after surgery leading up to approximately 4 years of age.

Aim 3: Will assess neurodevelopmental test results in craniosynostosis patients and seek to *correlate* these findings with white matter tract changes.

Title: Neurodevelopmental Outcomes in Craniosynostosis Repair
PI: [name]
Site: Arkansas Children's Hospital
Funding: UAMS Intramural Grant

Study Population

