This will be a prospective, longitudinal observational study. Prospective subjects will come from those patients seen as they present to the plastic and/or neurosurgery clinics and a diagnosis of craniosynostosis is suspected. Subsequently, if surgery is indicated, these patients will be approached and considered for inclusion the study. Of note, regardless of study participation it is our practice to follow children with CVR annually until the age of skeletal maturity, i.e., between 16-18 years of age. Annual visits may include but are not limited to the clinic exam, imaging, neurodevelopmental testing and or laboratory blood work, all of which are part of the standard of care for children with craniosynostosis.

We estimate that the duration of this study to be completed by December 31, 2030. We intend to include up to 500 subjects diagnosed with craniosynostosis and up to 60 normal control subjects in this study. The normal control subjects will undergo only a single MRI without sedation, using previously published calming techniques ¹³ and a single Bayley and/or Mullen Scales (age appropriate) administered just prior to the MRI. If the child is deemed within normal limits, they can proceed to the MRI imaging.. We plan to recruit normal, age-matched controls with an awarded UAMS Research Scholar Pilot grant. We will recruit control patients from our neurosurgery and plastic surgery clinics. These patients will be chosen amongst healthy children as stated in the inclusion /exclusion criteria. We expect these patients to be mostly patients who are referred to our clinic with abnormal head shapes due to position but does not have craniosynostosis or any related health problems.

Inclusion Criteria

- Up to 500 children, for all subjects, age of initial study entry: one test group between 3-6 months old (endoscopic assisted), and the other 6-24 months of age (open CVR)) once enrolled, children will be included until 4 years of age.
- Diagnosed with craniosynostosis, single or multiple suture
- Babies with craniosynostosis syndrome including but not limited to Pfeiffers, Aperts, Cruozons, Muenkes.

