- Approximately 60 age-matched **controls** (3 in each group) not diagnosed with craniosynostosis syndrome, stratified by age groups starting at 3 months, 5 months, 7 months, 9 month 11 months, 13 months, 15 months, 17 months, 19 months, then every 3 months, 22 months, 25 months, 28 months, 31 months, 34 months, 37 months, 40 months, 43 months, 46 months, 49 months.

Title: Neurodevelopmental Outcomes in Craniosynostosis Repair
PI: [name]
Site: Arkansas Children's Hospital
Funding: UAMS Intramural Grant

Exclusion Criteria

- Children not meeting the inclusion criteria
- Children with traumatic brain injury, brain cancer, or VP shunt that could affect development.
- Children who have already undergone CVR repair
- **Developmentally Normal children who cannot undergo or cannot be still for an awake or asleep non-sedated MRI**

Study Design and Procedures

This observational study intends to collect all available patient data, including but not limited to:

- Age
- Date of birth
- Sex
- Race
- Ethnicity
- Physical Examination
- Personal Medical History
- Family Medical History
- Presenting clinical status
- Craniosynostosis type
- Present surgical history and procedures
- Inpatient Progress notes
- Discharge summaries
- Clinic notes
- Other interventions
- All Laboratory Results
- All Imaging Results
- Neurodevelopmental Assessments

Title: Neurodevelopmental Outcomes in Craniosynostosis Repair
PI: [name]
Site: Arkansas Children's Hospital
Funding: UAMS Intramural Grant

Radiological Component

Standard-of-care at ACH and at other institutions is initial imaging to confirm the diagnosis of craniosynostosis and identify any other intra-cranial abnormalities. This initial imaging can be in the form of either a low-dose radiation computed-tomography (CT) of the head or a MRI. Post-operative imaging, either CT or MRI, is based on clinical indicators and not routinely performed on all patients. Once the patient is identified and consented for the study, we will implement an MRI-based protocol to look at both the bone and the brain, thus obviating the need for a CT scan, however, in some cases a CT scan may need to be obtained or have been obtained at an outside facility.

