component for test subjects who, for developmental or behavioral reasons, could not successfully complete an imaging study necessary for diagnosis and completion of the study. We will carefully detail the risks of performing the MRI under sedation as expanded in the risks section below. One Pre-operative MRI is clinically indicated to establish and confirm the diagnosis and the three post-operative MRI's will be done for research purposes.

Surgical Component (Plastic Surgery & Neurosurgery)

Once patients are identified and surgery is planned, the standard of care procedures fall into two categories based on age of presentation and clinician judgement and family preference all other things being equal. Both the endoscopic-assisted craniectomy and open CVR are standard of care procedures performed at every major craniofacial center. The ideal candidate for endoscopic-assisted craniectomies are infants with confirmed craniosynostosis (typically sagittal) who present at an age in which they can be operated on within 3-6 months of age. The ideal candidate for open CVR is any patient with confirmed craniosynostosis in which surgery can be performed after 6 months old. It has been our experience that these patients self-select into these groups solely by what age they present to our clinic. None of the surgery performed nor any aspect of the surgery is experimental.

Neurodevelopmental Assessment Component

Under direction of [name] and her teams routinely examine patients with craniosynostosis both pre-operatively and post-operatively as part of American Cleft palate craniofacial Association (ACPA) guidelines and standard of care. Thus, these examinations are part of the normal clinical exam and part of the medical record. The Bayley Scales of Infant and Toddler Development are used up to and including age 4 and the Mullen Scales of Early Learning are used from birth to 68 months.

Control Group Neurodevelopmental Assessment

Control subjects will be tested by ACH but if published MRI and developmental testing are readily available and sufficient for data analysis that will be used instead of enrolling control patients.

Schedule of Imaging and Neurodevelopmental Assessment

1. **PRE- OP** Within 30 days of the surgery date (all 3 components may occur on the same day or different days for family convenience):

Title: Neurodevelopmental Outcomes in Craniosynostosis Repair
PI: [name]
Site: Arkansas Children's Hospital
Funding: UAMS Intramural Grant

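### A clause letting published data replace enrolled controls contradicts the rest of the protocol and could confound the patient/control level comparison with data source

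*Combined protocol and SAP*

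**What the plan says.** The combined protocol and SAP gives two accounts of where controls come from.

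- **Own controls, with public data added.** Relevant Literature and Data says "we will plan to recruit our own control subjects, age matched to our test subjects, but also plan to compare them" with public data sets once these become available. Aim 1 is to build a normative white-matter curve from pilot data. Aim 2 compares patients with the Aim 1 controls, "pooled with other centers and compared with published data sets of normal babies from the Baby Connectome Project". Study Population plans "up to 60 normal control subjects in this study" and adds: "We plan to recruit normal, age-matched controls with an awarded UAMS Research Scholar Pilot grant". Radiological Component states that controls have the same MRI protocols as patients.
- **Public data replacing own controls.** Control Group Neurodevelopmental Assessment starts from local testing as the default, then says that "if published MRI and developmental testing are readily available and sufficient for data analysis that will be used instead of enrolling control patients". Although the heading concerns testing, the sentence names MRI. It does not say what counts as sufficient, who decides, or when.

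Endpoint 1 is a DTI comparison of patients with age-matched controls. Statistical Methods leaves that comparison to unspecified standard methods. The only MRI-session variable it names is sedation. It has no term for scanner, site or data source, and no harmonisation step.

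**The concern.** Both accounts cannot be followed. Once its condition is met, the replacement sentence reads as a direction, and the condition could plausibly be met because the protocol already expects to use a public infant imaging data set.

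If the sentence were applied in full and nobody in the collaboration scanned controls, every control would come from outside the study and every patient from inside it. Any systematic difference in scanner, sequence or test administration between the two sources would then appear as a difference between patients and controls. At stake are endpoint 1, the control part of Aim 2, and further own-site data for Aim 1.

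**Working it through.** **1. The plan's control count.** Inclusion Criteria lists 19 ages from 3 to 49 months, with 3 controls at each: 19 × 3 = 57. The plan says approximately 60 there and up to 60 in Study Population. Given that wording, 57 is consistent and not a fault. I also use 57 as the size of an external control set. That is an assumption, because the documents give no size for one.

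**2. Can the group effect be separated from data source?** Let G = 1 for a patient and 0 for a control, S = 1 for external data and 0 for study data, F = field strength (1.5T or 3T), A = age. The model is

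y = b0 + b1·G + b2·S + b3·F + b4·A + error.

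If all patients are in the study and all controls are external, S = 1 − G for every child. Substituting gives

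y = (b0 + b2) + (b1 − b2)·G + b3·F + b4·A + error.

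Only b1 − b2 can be estimated, that is, the group effect minus the source offset. A design-matrix check agrees:

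- External controls only: 5 columns, rank 4, so not estimable.
- Own controls only: no source column is needed; 4 columns, rank 4, so estimable.

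A larger sample or another covariate does not help. Nor do indicators for several study centres while every control is external, because G is then the sum of those indicators.

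**3. What an offset would do.** With no true difference, the expected group difference equals the offset d in size. In SD units, with two-sided 5% alpha,

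SE = √(1/patients + 1/controls)

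P(false difference) = Φ(d/SE − 1.96) + Φ(−d/SE − 1.96).

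The plan's upper limit is 500 patients ("We intend to include up to 500 subjects diagnosed with craniosynostosis"). The lower value of 60 is an assumption.

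- 60 patients: SE = √(1/60 + 1/57) = 0.185
- 500 patients: SE = √(1/500 + 1/57) = 0.140

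Example for d = 0.2 and 60 patients: 0.2/0.185 = 1.08, so Φ(−0.88) + Φ(−3.04) = 0.190 + 0.001 = 0.191.

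| Offset (SD, assumed) | 60 patients | 500 patients |
|---|---|---|
| 0 | 5% | 5% |
| 0.1 | 8% | 11% |
| 0.2 | 19% | 30% |
| 0.3 | 37% | 57% |
| 0.5 | 77% | 95% |

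**4. With study-scanned controls kept.** Assuming 500 patients and an even split between the two study scanners:

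- 57 own controls: full rank, SE of the group effect 0.14 SD.
- 57 own plus 57 published, with a source term: full rank, SE 0.14 SD.
- 19 own (one per age) plus 57 published, with a source term: full rank, SE 0.23 SD, matching √(1/500 + 1/19) = 0.234.

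Once a source term is fitted, the precision of the level comparison is set almost entirely by the number of study-scanned controls.

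**The case against.** The strongest reply is that the worst case needs several things to happen together, and the documents do not say that they will.

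- **The rule is conditional.** Local testing is the default, public data are described as a future resource, and funding for controls is already awarded. The heading on compensation refers to new and existing subjects and controls, which may mean that some controls were already enrolled, although the word for existing may apply to subjects only. The clause stops enrolment; it does not discard children already scanned. Any study-scanned control breaks the exact alias.
- **Patients do not all come from one site.** The introduction describes a three-centre collaboration, and Study Aims and the data-handling section plan pooling. A reader might infer that group would be identical to site and scanner. The documents do not support that. If a partner scans its own controls, the alias with data source is also incomplete. However, no partner is required to do so, and their protocols are described as similar or identical, so the same clause may apply there.
- **Different image processing is not documented.** Public images might be reprocessed locally.
- **No offset is documented.** Rates close to certainty need a large assumed offset, or a large external control set that the plan does not mention. At 0.1 SD the inflation is modest.
- **Deletion is not the only remedy.** Defining sufficiency and a minimum number of study-scanned controls would also break the alias.

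All of this stands, and it limits the reach of the point. It does not remove the contradiction, and Statistical Methods contains nothing that would limit the damage if the clause were used.

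**Conclusion.** The point holds in a conditional form. The replacement clause contradicts the control plan stated elsewhere. If it were fully applied with no local or partner-site controls scanned, the patient/control difference in level would be inseparable from any study-versus-external offset, and the bias would equal that offset whatever its size. The false-positive rates above illustrate this under stated assumptions (57 external controls, 60 to 500 patients, two-sided 5% alpha, no true difference, assumed offsets). They do not estimate what will happen.

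Two stronger readings are tempting and should be resisted. The first is that the study's results would be uninterpretable. Only the level comparison in endpoint 1 and the control part of Aim 2 is exposed. Within-patient change before and after surgery and the Aim 3 correlation do not directly use control levels, and a comparison of age slopes could partly survive a constant offset. The second is that Aim 1 would have no own-site data. The documents support only that it would gain no further own-site data once enrolment stopped.

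**What to change.** Delete the part of the sentence under Control Group Neurodevelopmental Assessment that lets published data take the place of enrolment. State there that controls scanned and tested under the study protocol are the primary comparator, as in Aims 1 and 2. Allow published data only as a supplementary comparison. In Statistical Methods, add a data-source term for that comparison, estimated through the study-scanned controls over the ages that both sources cover, and report results with and without the published data.

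The cost is that the option to save control recruitment is lost, and a little analysis work and text are added, since Statistical Methods has no such step now. Recruitment is already planned and the pilot grant awarded, so the change mainly restores what the other sections promise. Published data will add little precision to the level comparison, so they should not be counted on to reduce the number of study-scanned controls.

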Presurgical MRI will be done on a 3T MRI (Prisma Siemens MRI scanner) or 1.5T (Achiva, Phillips MRI scanner). The protocol for patients less than 18 months of age will be Sagittal T1, Axial inversion recovery (IR), T2, fluid-attenuated inversion recovery (FLAIR), susceptibility weighted image (SWI), diffusion weighted images (DWI), diffusion tensor imaging (DTI), resting state fMRI, and sagittal 3D GRE / FFE (on 1.5 T scanners) or 3D T1 VIBE (on 3T scanner).

The MRI protocol for patients over 18 months of age will be: Sagittal T1, coronal T2, Axial T2, fluid-attenuated inversion recovery (FLAIR), susceptibility weighted image (SWI), diffusion weighted images (DWI), diffusion tensor imaging (DTI), resting state fMRI, and sagittal 3D GRE / FFE (on 1.5 T scanners) or 3D T1 VIBE (on 3T scanner).

Post-processing of the acquired 3D GRE, FFE and T1VIBE sequences will be done on vitrea station. The acquired images will be reviewed by US board-certified pediatric neuroradiologists for single or multi suture craniosynostosis. Intracranial volume, ventricular size and sulcal crowding will be accessed. The DTI data will be analyzed on a password protected workstation by MRI physicist (Co-investigator, [name] and his research assistant, [name]) for evaluation of white matter microstructural integrity. Other imaging data from the same MRI sequences may also be exported to the workstation for additional quantitative analysis.

The expected time for MRI image acquisition is approximately 60 minutes for control subjects. If this process is prolonged greater than 2 hours due to control subject's lack of cooperation or discomfort then it will be aborted and will be re-scheduled. If the parents do not wish to proceed with a rescheduled time then the control subject will be removed from the study.

The MRI protocols will be identical for the control subjects and scheduled at the parent's convenience, but falling within one week on either side of their requested age. Because scheduling of the MRI may not allow this degree of control, control patients will be stratified by the age when they actually undergo the study not the age of recruitment. We will not plan to sedate the normal control subjects, however, sedation *may be a*

Title: Neurodevelopmental Outcomes in Craniosynostosis Repair
PI: [name]
Site: Arkansas Children's Hospital
Funding: UAMS Intramural Grant

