sedation, if and only if non-pharmacologic techniques do not produce a state in which the radiologist ([name]) thinks a high-quality image can be generated. Our team will attempt the non-sedation techniques first and if a child does need sedation to successfully complete the imaging study, the following risks will apply and be explained in the consent to the parents including: administration of medications for anesthesia including inhaled sevoflurane, intravenous propofol which have known side effects of nausea, vomiting, tachycardia, respiratory obstruction, hemodynamic instability, cough or laryngospasm. In addition other known complications of using a controlled airway, i.e., laryngeal mask airway (LMA) for children > 1 year old and endo-tracheal tube for < 1 year old, include tooth or mucosal injury, malignant hyperthermia, allergic reaction to an agent given.

There is also the risk associated with putting in performing intravenous (IV) access and these risk are typically infiltration of saline or anesthetic agents such as propofol into the skin or hematoma and/or bruising. There is also a risk of multiple sites puncture wounds, if a child if intra-venous access proves difficult. If for whatever reason the imaging study can not be performed within a reasonable parental expectation then the child will not be included in the study, but continue clinical care regardless.

All these common risks will be explained to the parents and if a side-effect or complication occurs, all treatment will be administered by the anesthesia team and the study coordinator and PI's will be notified and the IRB through our data-safety monitor within 24 hours of occurrence.

The potential risk of the MRI itself is the risk of causing anxiety in the patients and families and we plan to adopt the following measures borrowed from the techniques described from the investigators of the NIH funded Baby Connectome Project ¹³ for non-sedated MRI included but not limited to a tour of the MRI area prior to the scheduled MRI to familiarize the child and parents with the scan experience, prepping the parents with the headphones the child will wear, use of attenuating foam on the scanner, sandbags to reduce vibrations, dim lights, and pre-selected movies for the awake scans for the child.

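### The rule tying a child's inclusion to a successful scan names no visit, conflicts with retention to age 4, and has no missing-scan plan behind it

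*Combined protocol and SAP*

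**What the plan says.** **The rule for patients.** In Risks and Benefits, after the sedation and intravenous-access risks, the protocol says that if, whatever the reason, the "imaging study can not be performed within a reasonable parental expectation then the child will not be included in the study"; clinical care continues. No visit is named, and nothing is said about data already collected.

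**Retention.** The Inclusion Criteria say: "once enrolled, children will be included until 4 years of age".

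**Scans.** The Radiological Component says: "One Pre-operative MRI is clinically indicated to establish and confirm the diagnosis and the three post-operative MRI's will be done for research purposes".

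**Sedation.** The same section says sedation may be a "component for test subjects who, for developmental or behavioral reasons, could not successfully complete an imaging study". Risks and Benefits gives the order, unsedated first: "Our team will attempt the non-sedation techniques first and if a child does need sedation to successfully complete the imaging study", the listed anaesthetic risks apply.

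**Controls.** There is no sedation. The Exclusion Criteria leave out "Developmentally Normal children who cannot undergo or cannot be still for an awake or asleep non-sedated MRI". After an aborted scan, "If the parents do not wish to proceed with a rescheduled time then the control subject will be removed from the study".

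**Analysis.** The endpoints are DTI in patients against controls, DTI before and after surgery, and the relation of DTI to cognitive testing. Statistical Methods lists a paired t-test and a repeated measures analysis of unspecified form, with sedation as a variable for each MRI session. It names no analysis set, rule for missing scans, comparison of scanned with unscanned children, or sensitivity analysis.

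**The concern.** All three endpoints depend on which children have scans. A rule that makes inclusion depend on scan success selects the analysed group on something that may be related to the outcome. The protocol itself gives developmental or behavioural difficulty as the ground for sedation. The rule follows the sedation risks, so it governs children who remain unscanned although sedation is available.

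If it applies after enrolment, it also takes out children who already have a pre-operative scan and test scores that a longitudinal model could use. At stake are the level of DTI and development in the retained patients, the contrast with controls, and the strength of the DTI-development relation.

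**Working it through.** **1. Which visit does the rule cover?** The surrounding text deals with anaesthesia for the research MRIs. The section later frames the issue as up to three additional post-operative MRIs and places sedation at an older, post-operative age. That points to follow-up scans. The wording itself can also be read as an entry rule, and the Inclusion Criteria keep enrolled children to age 4. A child with a failed post-operative scan is out under one passage and in under the other.

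**2. How many children might be lost?** The documents give no rate; 500 is a ceiling. Assume a share p fails unsedated and sedation rescues a share s. Final loss = p(1 − s).

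| p | s = 0 | s = 80% | s = 95% |
|---|---|---|---|
| 10% | 10% (50 of 500) | 2% (10) | 0.5% (2.5) |
| 30% | 30% (150) | 6% (30) | 1.5% (7.5) |
| 50% | 50% (250) | 10% (50) | 2.5% (12.5) |

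If the rule bites at any of three post-operative scans, loss accumulates. A 2% loss per scan, independent between scans, gives 1 − 0.98³ = 5.9%.

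**3. Shift in level of a developmental score.** Assume failure occurs above a cut-off of a normal propensity that correlates r with poorer development. With final loss f, the retained mean rises by r × λ SD, where λ = φ(z)/(1 − f) and z is the upper-f normal quantile.

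| f | z | φ(z) | λ | r = 0.3 | r = 0.5 |
|---|---|---|---|---|---|
| 2% | 2.054 | 0.0484 | 0.0494 | 0.015 SD, 0.2 points | 0.025 SD, 0.4 points |
| 6% | 1.555 | 0.1191 | 0.1267 | 0.038 SD, 0.6 points | 0.063 SD, 1.0 points |
| 10% | 1.282 | 0.1755 | 0.1950 | 0.058 SD, 0.9 points | 0.097 SD, 1.5 points |

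Points are SD × 15, an assumed scale SD. If r = 0 the shift is zero.

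**4. DTI level and correlation.** Assume one severity factor drives both fractional anisotropy (FA) and development, with true correlation ρ = 0.30, and that exactly the most severe are lost (the extreme case). The FA shift is √0.30 × λ. The variance of severity among the retained is v = 1 − zλ − λ², and the correlation becomes ρv/(ρv + 1 − ρ).

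- 2% loss: shift 0.548 × 0.0494 = 0.03 SD; v = 0.896; correlation 0.269/0.969 = 0.28.
- 10% loss: shift 0.548 × 0.195 = 0.11 SD; v = 0.712; correlation 0.214/0.914 = 0.23.

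A simulation of 2,000,000 draws agrees. With a milder link (odds ratio 2 of loss per SD of severity), 10% loss gives only +0.04 SD and a correlation of 0.29. With loss unrelated to severity, nothing moves.

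**5. Before-after change.** A removed child drops out of both the before and the after mean, so the same children are compared at each visit. The mean change then shifts by r_c × λ, where r_c is the correlation of failure with poorer change. Selection on level alone (r_c = 0) gives no bias. With r_c = 0.3 and 10% loss it is 0.3 × 0.195 = 0.06 SD of change.

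**The case against.** **Sedation is aimed at the children in question.** The phrase about developmental or behavioural reasons describes who may be sedated, not who is lost. A reader might infer that the rule removes the most affected children. The documents do not say so: those left out are families who decline or stop and children who cannot be scanned even with sedation, and their severity is unknown. This stands, and it is why the loss may be small. It does not settle the matter, because children for whom sedation is declined or unsuccessful may come disproportionately from the group described as "for developmental or behavioral reasons, could not successfully complete an imaging study necessary for diagnosis and completion of the study".

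**The rule may apply only at entry.** This is possible. The schedule also labels the pre-operative functional sequences research-related, so the text on research MRIs need not concern follow-up alone. The conflict with the retention statement remains until the protocol says which is meant.

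**Nothing says collected data are discarded.** Correct. The protocol intends to collect all available patient data, and the repeated measures analysis might use partial records. But neither point is spelled out, and a child not included in the study would ordinarily not be analysed.

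**The apparent benefit of surgery.** A reader might infer that the mean improves over time as the worst drop out, which would favour surgery. Under this rule it does not follow, for the reason in step 5 of the working. Such drift would need the lost children's baselines kept and raw means compared visit by visit.

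**Controls are selected too**, more strictly: unsedated only, after a normal developmental test. If that selection is also related to development, it acts on the other side of the patient-control contrast. Keeping test scores of unscanned controls would not help, as controls serve the DTI curve.

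**Conclusion.** The point holds in limited form. Inclusion depends on a successful scan, the visit is not stated, the text conflicts with retention to age 4, and the analysis plan has nothing for missing scans. These follow from the documents.

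The direction of bias is conditional. If loss is related to severity, and more severe patients have lower FA and scores, the retained patients look better, the patient-control difference shrinks (taking controls as given) and the DTI-development correlation weakens. The before-after change is biased only if failure is related to the change itself.

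The size is unknown. On a developmental score the shift is about 0.2 to 0.4 points at 2% final loss and 0.9 to 1.5 points at 10%, for an assumed r of 0.3 to 0.5 and SD of 15. These figures concern the level of a developmental score, not a DTI endpoint. The illustrative DTI figures rest on a further assumed model. The correction should be made because it is cheap and reasons for missed scans are hard to reconstruct later, not because a large bias has been shown.

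**What to change.** 1. Reconcile the Risks and Benefits sentence with the Inclusion Criteria. Possible wording: *Once enrolled, a child whose research scan fails or is declined stays in the study unless consent is withdrawn. The scan is recorded as missing, with the visit and the reason. All completed scans and developmental tests are analysed.* This leaves sedation practice, clinical care and the parents' right to decline unchanged.
2. In Statistical Methods, replace paired tests on completers with a likelihood-based mixed model on all available scans and tests. This matters once partial records are kept, since raw visit means could then drift with dropout.
3. Report baseline developmental score and syndrome status of children with and without each scan, with counts and reasons.
4. Optionally, add a sensitivity analysis for severity-related missing scans.

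The cost is a protocol sentence and a little more analysis. There may also be some developmental testing of unscanned children: the Neurodevelopmental Assessment Component calls testing standard care, but the schedule labels it research-related at the post-operative visits.
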